#### 7.0 Statistical Analysis Plan

#### 7.1 Primary End Point

The primary end-point of the study is the safety of delivering SBRT to the prostate. The dose and fractionation of radiation is determined such that the risk of late complications should be equivalent to the  $BED_{3Gy}$  of 78 Gy in 2 Gy fractions.

A conservative estimate of grade 3 rectal toxicity for this regimen of 78 Gy in 2 Gy fractions is 1.5% at 2 years. Therefore, with a patient population of 60 patients if the true rate of grade 3 or higher rectal toxicity is 1.5% there will be a 77% power to rule out a >7.1% rate. If the true rate is 2.5%, there will be an 81% power of ruling out a >9.6% rate.

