# 7.4 Stopping Rules for Excessive Adverse Events

We estimate  $\leq 7.5\%$  of the men will experience a grade 3+ adverse event. For this study, a rate of 5% grade 3+ GU and GI adverse events (pt) according to the CTCAE version 4.0 within 24 months of the start of radiation therapy is considered acceptable. A rate of 20% is considered unacceptable. The null hypothesis (H0) is that this radiation therapy is not tolerable versus the alternative hypothesis (HA) that this radiation therapy is tolerable. With 60 patients the power to reject the null hypothesis is >90%.

The stopping and continuation rules in the Table below will be applied in two stages to the first analyzable 30 cases who received at least some treatment. Analyzable patients are defined as eligible patients who received at least some treatment. If at any stage, we show that the grade 3+ GU and GI adverse event rate may be greater than or equal to 20%, we would temporarily close the study to accrual, gather the relevant source data on the cases with grade 3+ GU and GI adverse events, prepare a statistical report summarizing the adverse event findings, and present the report to the radiation oncology and GU multidisciplinary team for review. The GU team will review all source documentation on the analyzed cases with adverse events and the statistical report summarizing the findings as soon as possible. Following the review of the data, the team will discuss the findings and make a recommendation about the study. If at the first or second stage either of the stopping rules is not met, we will continue accrual and monitoring for grade 3+ GU and GI adverse events. If we continue until the last stage, then we will either conclude "tolerability" or not.

Number of Analyzable Patients *	Reject H0 pt $\ge$ 0.2 and continue	Reject HA : $pt \le 0.05$ and stop		
15	≤2	≥ 3		
30	≤ 3	$\geq 4$		

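### Section 7.4 attaches a final tolerability conclusion to a 30-man monitoring table, although safety is the primary end-point of a 60-man trial

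*Combined protocol and SAP*

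**What the plan says.** Section 7.1: "The primary end-point of the study is the safety of delivering SBRT to the prostate". It takes 1.5% at 2 years as a conservative grade 3 rectal toxicity rate for the conventional comparator regimen. For 60 men with that true rate, "there will be a 77% power to rule out a >7.1% rate". It adds: "If the true rate is 2.5%, there will be an 81% power of ruling out a >9.6% rate". No alpha, success cut-off or choice between the two bounds is given.

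Section 7.4 concerns a wider event: it takes as acceptable "a rate of 5% grade 3+ GU and GI adverse events (pt) according to the CTCAE version 4.0" within 24 months of starting radiation. "A rate of 20% is considered unacceptable". The null hypothesis is that treatment is not tolerable and the alternative that it is; power is put above 90% with 60 patients. The table is applied to the first 30 analyzable men: at 15, continue with 2 or fewer events and stop with 3 or more; at 30, continue with 3 or fewer and stop with 4 or more. Its favourable column is labelled as rejecting the null. Crossing a boundary leads to temporary closure, review of source data and a team recommendation. The section then says "If we continue until the last stage, then we will either conclude" tolerability or not.

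Section 3.1 names a different primary end-point: grade 2+ late toxicity at 2 years.

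**The concern.** A finding that treatment is tolerable with respect to grade 3+ GU and GI events is a safety conclusion. Section 7.4 is the only place in the plan with explicit hypotheses and a printed pass/fail count, and the printed counts end at 30 men. Nothing makes that conclusion subordinate to the primary safety end-point in 60 men, or says that the table governs accrual only.

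Two consequences follow if the section is applied as printed. A favourable statement can be issued from half the planned men, and later events cannot change it. And because grade 3+ rectal events are a subset of grade 3+ GI events, that statement can appear beside a 7.1 analysis that has not excluded its rectal bound, with no text saying which of them is the trial's safety result.

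**Working it through.** **Inputs.** From 7.1: N = 60; true rectal rate 1.5% paired with the 7.1% bound (power 77%); 2.5% paired with 9.6% (power 81%). From 7.4: acceptable 5%, unacceptable 20%, expected overall grade 3+ rate at most 7.5%, table ≤2/15 then ≤3/30, power above 90%. Assumptions: men are independent and every man counted has complete 24-month status.

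**1. Reproducing 7.1.** One-sided 95% score upper limit, z = 1.645:

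U(x, n) = [p + z²/(2n) + z·√(p(1−p)/n + z²/(4n²))] / (1 + z²/n), with p = x/n.

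- U(1, 60) = (0.0167 + 0.0226 + 1.645 × 0.02147)/1.0451 = 7.13%, and P(X ≤ 1 | 60, 1.5%) = 77.3%.
- U(2, 60) = 9.58%, and P(X ≤ 2 | 60, 2.5%) = 81.0%.

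Both stated pairs are matched, so cut-offs of ≤1/60 and ≤2/60 are a well-supported inference. They remain an inference, since 7.1 prints neither. Exact (Clopper-Pearson) one-sided limits, 7.66% and 10.12%, do not match.

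**2. Reproducing 7.4.** Probability of passing both looks at true rate p:

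P(pass) = Σ over a = 0, 1, 2 of P(A = a) × P(B ≤ 3 − a), with A and B each binomial(15, p).

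- p = 5%: 0.4633 × 0.9945 + 0.3658 × 0.9638 + 0.1348 × 0.8290 = 92.5%. The stated power above 90% is met by the 30-man table alone.
- p = 20%: 0.0352 × 0.6482 + 0.1319 × 0.3980 + 0.2309 × 0.1671 = 11.4%. This is the chance of concluding tolerability at the unacceptable rate.

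**3. What a bare pass shows.** The observed rate is 3/30 = 10%, and U(3, 30) = (0.1 + 0.0451 + 1.645 × 0.06125)/1.0902 = 22.6%. A bare pass therefore does not exclude 20% at the one-sided 95% level. The exact limit is 23.9%.

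**4. Tolerability concluded while 7.1 is not met.** Take 7.5% overall and let r be the rectal rate. A man with an event has a rectal one with probability q = r/7.5%. Sum over all (a, b) that pass step 2:

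P(a) × P(b) × P[Bin(a + b, q) + Bin(30, r) > c],

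where the second binomial is men 31 to 60 and c is the inferred 7.1 cut-off.

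- r = 1.5% (q = 0.20), c = 1, bound 7.1%: 14.7%.
- r = 2.5% (q = 0.33), c = 2, bound 9.6%: about 11%.

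For scale, 7.1 misses its own bound in 100 − 77.3 = 22.7% and 100 − 81.0 = 19.0% of trials at these true rates.

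**5. If the last stage means 60 men.** No cut-off is printed. Power above 90% at 5% would need at least 5/60: P(X ≤ 4 | 60, 5%) = 82.0%, P(X ≤ 5 | 60, 5%) = 92.1%, with P(X ≤ 5 | 60, 20%) = 1.2%.

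**The case against.** The best defence is that 7.4 is monitoring and nothing else. Its heading and table title say so, the favourable column tells the team to continue even at 30 men, and an adverse crossing leads only to a pause and a review. A monitoring boundary looser than the primary bound is normal practice. This stands: neither the boundary nor its looseness is an error. It does not explain the hypotheses, the power claim or the closing conclusion, none of which a pure accrual rule needs.

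Second, the last stage may mean 60 men: the text has accrual and monitoring continuing after the first or second stage, and the power sentence cites 60 patients. That reading is fair, and the 11.4% and 22.6% figures do not apply to it. But it leaves the conclusion with no printed criterion.

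Third, a reader might infer that 7.1 and 7.4 are two rival verdicts in direct conflict. The documents do not support that. Section 7.1 states no alpha or cut-off, and the end-points are nested but different, so a 7.4 excess made up of GU events beside a low rectal rate is no contradiction. Counting such reverse cases, and crossing 7.1's pairings of true rate and bound, would give disagreement in 27% to 37% of trials; that overstates the problem.

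**Conclusion.** The point holds in a limited form. As printed, 7.4 allows a final tolerability conclusion from the first 30 men, independent of men 31 to 60, with an 11.4% chance at the unacceptable 20% rate and an upper limit of 22.6% on a bare pass. These two figures rest on the 30-man reading and complete 24-month status.

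The overlap with 7.1 is secondary. It amounts to about 15% and 11% of trials, given 7.5% overall, 7.1's own pairings and the inferred cut-offs. Because the true rectal rates there are the favourable ones, those cases reflect 7.1's limited power rather than a false safety claim by 7.4.

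A reader might also set the 7.4 pass probability at a true 7.1% rate (81.7%) against that of the inferred 7.1 rule (6.7%). That contrast needs every grade 3+ event to be rectal. The plan expects 1.5% rectal against up to 7.5% overall, so it should not be taken as the size of the problem.

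**What to change.** - First reconcile the primary end-point between 3.1 (grade 2+ late toxicity) and 7.1 (grade 3+ rectal toxicity). The remaining wording depends on it; what follows takes the 7.1 end-point.
- In 7.4, state that passing the 15- and 30-man looks means only that accrual and monitoring continue. Remove the tolerability conclusion from that table, and align the column label and power sentence with this. The boundaries can stay as they are.
- In 7.1, state that the safety conclusion is drawn once, from all treated patients, against one named bound, with its alpha and cut-off printed.
- Report the 24-month grade 3+ GU/GI rate with its confidence interval in all treated men as supportive.
- If a formal test of 20% against 5% is kept, base it on all 60 men. For example, a single-look cut-off of ≤6/60 gives P(X ≤ 6 | 60, 5%) = 97.0% power and P(X ≤ 6 | 60, 20%) = 3.1% error, ignoring the earlier looks. Its score upper limit is 18.2%; at 7/60 it is 20.2%.
- Do not make a crossed 7.4 boundary an automatic bar to a safe conclusion: 7.4 makes it a trigger for review. Requiring both would also lower the chance of a favourable result from 77% to about 65% at 7.5% overall and 1.5% rectal (79.2 − 14.7 = 64.5%).

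Cost: short edits to 3.1, 7.1 and 7.4, with no added patients or data. The trial gives up a formal tolerability claim after 30 men.

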#### Stopping and Continuation Rules for Grade 3+ GU/GI Adverse Events

\* Analyzable patients are defined as eligible patients who received at least some treatment.

# 9.0 Appendices

Appendix 1	AJCC Staging System 6th edition
Appendix 2	The Expanded Prostate Cancer Index Composite (EPIC-26)
Appendix 3	SBRT Dosimetry Worksheet

#### 9.1 Appendix 1 AJCC Staging System – Prostate, 6th Edition

#### **DEFINITION OF TNM**

#### Primary Tumor, Clinical (T)

- TX Primary tumor cannot be assessed
- T0 No evidence of primary tumor
- T1 Clinically inapparent tumor not palpable or visible by imaging
  - T1a Tumor incidental histologic finding in 5% or less of tissue resected
  - T1b Tumor incidental histologic finding in more than 5% of tissue resected
  - T1c Tumor identified by needle biopsy (e.g., because of elevated PSA)
- T2 Tumor confined with prostate\*
  - T2a Tumor involves less than  $\frac{1}{2}$  of one lobe
  - T2b Tumors involves greater than  $\frac{1}{2}$  of one lobe but < 2 lobes
  - T2c Tumor involves both lobes
- T3 Tumor extends through prostate capsule\*\*
  - T3a Extracapsular extension (unilateral or bilateral)
    - T3b Tumor involves the seminal vesicle(*s*)
- T4 Tumor is fixed or invades adjacent structures other than the seminal vesicles: bladder neck, external sphincter, rectum, levator muscles and/or pelvic wall

\*Note: Tumor found in one or both lobes by needle biopsy, but not palpable or reliably visible by imaging, is classified as T1c

\*\*Note: Invasion into the prostatic apex or into *(but not beyond)* the prostatic capsule is not classified as T3, but as T2.

#### **Regional Lymph Nodes (N)**

Clinical

NX Regional lymph nodes cannot be assessed

- N0 No regional lymph node metastasis
- N1 Metastasis in regional lymph node or nodes

#### Pathologic

pNX Regional nodes not sampled

pN0 No positive regional nodes

pN1 Metastases in regional node(s)

#### Primary Tumor, Pathologic (pT)

- pT2\*\*\* Organ confined
- pT2a Unilateral
- pT2b Bilateral
- pT3 Extraprostatic extension
- pT3a Extraprostatic extension
- pT3b Seminal vesicle invasion
- pT4 Invasion of bladder, rectum

\*\*\*Note: There is no pathologic T1 classification

#### Appendix 1 AJCC Staging System – Prostate Continued

#### Distant Metastasis\*\*\*\* (M)

- MX Presence of distant metastasis cannot be assessed
- M0 No distant metastasis
- M1 Distant metastasis
  - M1a Non regional lymph node(s)
  - M1b Bone(s)
  - M1c Other site(s)

\*\*\*\*Note: When more than one site of metastasis is present, the most advanced category is used. pM1c is most advanced

#### Histopathologic Grade (G)

- GX Grade cannot be assessed
- G1 Well-differentiated (slight anaplasia)
- G2 Moderately differentiated (moderate anaplasia)
- G3-4 Poorly undifferentiated or undifferentiated (marked anaplasia)

#### **Stage Grouping**

Stage I	T1a	N0	M0	G1
Stage II	Tla	N0	M0	G2, G3-4
	T1b	N0	M0	Any G
	T1c T1	N0 N0	M0 M0	Any G Any G
	T2	N0	M0	Any G
Stage III	Т3	N0	M0	Any G
Stage IV	T4	N0	M0	Any G
	Any T	N1	M0	Any G
	Any T	Any N	M1	Any G

#### 9.2 Appendix 2 EPIC-26

## **Expanded Prostate Cancer Index Composite Short Form**

#### EPIC-26 The Expanded Prostate Cancer Index Composite

#### Short Form

This questionnaire is designed to measure Quality of Life issues in patients with Prostate cancer. To help us get the most accurate measurement, it is important that you answer all questions honestly and completely.

Remember, as with all medical records, information contained within this survey will remain strictly confidential.

Today's Date (please enter date when survey completed): Month\_\_\_\_\_Day\_\_\_\_Year\_\_\_\_

Name (optional):

Date of Birth (optional): Month\_\_\_\_\_Day\_\_\_\_Year\_\_\_\_\_

1. Ove	r the past 4 weeks, how often ha	ave you l	eaked urine?				
	More than once a day		1				
	About once a day		2				
	More than once a week		3 (Circl	e one numb	er)		23/
	About once a week		.4				
	Rarely or never		5				
2. Whic	h of the following best describes	your urir	nary control du	uring the las	st 4 weeks?		
	No urinary control whatsoev	er		1			
	Frequent dribbling			2	(Circle one nu	umber)	26/
	Occasional dribbling						
	Total control			4			
3. How dur	many pads or adult diapers per o ing the last 4 weeks?	day did y	ou usually use	e to control le	eakage		
	None			0			
	1 pad per day			1			
	2 pads per day			2	(Circle one nu	umber)	27/
	3 or more pads per day			3			
4. How	big a problem, if any, has each o	f the folk	owina been fo	r vou during	the last 4 wee	ks?	
(	Circle one number on each line)			,			
	,	No	Very Small	Small	Moderate	Big	
-	Drinning of leaking uring	Problem	Problem	Problem	Problem 2	Problem	20/
a.	Dripping or leaking urine	0	1	2	3	4	28/
D.	Pain or burning on unnation	0	1	2	3	7	28/
с. 	Bleeding with unnation	U	1	2	3	-	30/
a.	weak unne stream			2		4	24/
	or incomplete emptying	~	1	2	3	-	31/
e.	the day	9		2	2	4	22/
	ule day	0		2	5	-	33/
5 Over	all, bow big a problem has your u	rinary fu	nction been fo	r you durine	the last 4 wee	aks?	
	No problem	,	1				
	Very small problem		2				
	Small problem		3	(Circle one	number)		34/
	Moderate problem		4	,	,		
	Big problem		5				
EPIC-SF 6.200	2 Copyright	2002. The	University of M	ichigan. All rig	hts reserved.		

#### Duke Prostate SBRT

									Mark in This Space

How big a pro

	oblem, if any, has each o	of the follow	ving been for y	ou? (Circ	e one r	number	on eac	h line)	
		No Problem	Very Small Problem	Small Problem	Mo P	derate roblem	E Pro	Big Iblem	
a. Urgend	y to have								
a bowe	movement	. 0	1	2		3		4	49/

b. Increase
	ed frequency of								
bowel i	novements	. 0	1	2		3		4	50/
c. Losing	control of your stools	0	1	2		3		4	52/
d. Bloody	stools	. 0	1	2		3		4	53/
e. Abdom	inal/ Pelvic/Rectal pain.	. 0	1	2		3		4	54/
7. Overall, how	big a problem have your	bowel hab	its been for yo	u during	the las	t 4 wee	eks?		
No	problem	1							
Ver	y small problem	2							
Sm	all problem		(	(Circle on	e numb	er)			55/
Mo	derate problem	4							
Big	problem								

 
How would y
 
	ou rate each of the folio	wing during	g the last 4 w	eeks? (Ci	ircie on	e numb	er on e	ach line)	
				Poor					
				to None	Poor	Fair	Good	Very Good	
- Verr	ability to have an execti	2					4		57/
a. Tour	ability to have an erecu	(aliman)?			2	2	4	5	50/
D. YOUR	ability to reach orgasm	(climax)?		1	2	3	4	5	58/
9. How would you describe the usual QUALITY of your erections during the last 4 weeks?									
None at all 1									
Not firm	Not firm enough for any sexual activity 2								
Firm enough for masturbation and foreplay only 3 (Circle one number)						59/			
Firm end	ugh for intercourse				4				

 
How would you describe the FREQUENCY of your erections during the last 4 weeks?
 
									
I NEVER had an erection when I wanted one 1									
I had an erection LESS THAN HALF the time I wanted one 2									
I had an erection ABOUT HALF the time I wanted one							60/		
I had an erection MORE THAN HALF the time I wanted one 4									
I had an erection WHENEVER I wanted one									

						Do Not Mark in This Space	
11. Overall, how would you rate your ability	to fund	tion sexually	during the l	ast 4 weeks?			
Very poor		1					
Poor		2					
Fair			(Circ	le one numbe	r)	64/	
Good		4					
Very good							
12. Overall, how big a problem has your set	xual fu	nction or lack	of sexual fur	uction been for	vou		
during the last 4 weeks?					,		
No problem		1					
Very small problem		2					
Small problem 3 (Circle one number)						68/	
Moderate problem 4							
Big problem							
big problem							
13. How big a problem during the last 4 weeks, if any, has each of the following been for you?							
(Circle one number on each line)							
	No	Very Small	Small	Moderate	Big Broblom		
E	robiem	riouen	rioveni	Frobern	riouen		
a. Hot flashes	0	1	2	3	4	74/	

b. Breast tenderness/enlargement
	0	1	2	3	4	75/	
c. Feeling depressed	0	1	2	3	4	77/	
d. Lack of energy	0	1	2	3	4	78/	
e. Change in body weight	0	1	2	3	4	79/	

THANK YOU VERY MUCH!!

# 9.3 Appendix 3 Data Collection: Dosimetry and Initial Evaluation

Patient	Initials: Subject Study	/ ID Number:	-
1.Prosta	ate volume (CTV)		сс
2.Prosta	ate planning target volume (PTV)		cc
3.Confo	ormality index (Volume of prescription isodose s	urface / volume of PTV)	
4. Minir	num dose to 1% of prostate planning target volu	me $(P + 0.3)$ .	Gy
5. Maxin	mum dose to 1% of prostate planning target volu	me(P+0.3) .	Gy
6.Mean	dose to the prostate planning target volume (P +	0.3)	Gy
7.Bladd	ler volume at time of planning CT		cc
8.Maxin	mal dose delivered to 2 cc or more of bladder		Gy
9.Perce	nt and absolute volume of bladder > 37 Gy (V10	0) %	cc
10.	Percent and absolute volume of bladder > 33 (	Gy (V90) %	cc
11.	Percent and absolute volume of bladder > 28	Gy (V75) %	cc
12.	Percent and absolute volume of bladder >24 C	iy (V65) %	сс
13.	Percent and absolute volume of bladder >18.5	Gy (V50) %	сс
14.	Mean dose to prostatic urethra		Gy
15.	Maximal dose to 10% of prostatic urethra	·	Gy
16.	Rectal volume at time of planning CT		cc
17.	Maximal dose delivered to 2 cc or more of rec		Gy
18.	Percent and absolute volume of rectum > 37 C	iy (V100)%	cc
19.	Percent and absolute volume of rectum $> 33$ C	у (V90)%	cc
20.	Percent and absolute volume of rectum $> 28$ C	ry (V75) %	cc
21.	Percent and absolute volume of rectum > 24 C	iy (V65) %	cc
22.	Percent and absolute volume of rectum > 18.5	Gy (V50) %	cc
23.	Mean dose to right femoral head	·	_ Gy
24.	Mean dose to left femoral head		_ Gy
25.	Energy	MV	Ţ
26.	Number of fields:		
27.	Non-axial beams?	Yes	or No
28.	Date of first fraction		
29.	Date of last fraction		_
30.	Elapsed time (days) from first fraction to last	fraction:	
31.	Institution Patient treated at:		
32.	Mode (Calypso=1, ExacTrac=2)		_

Age at time of enrollment Month and Year of birth Race Zip code Date of Prostate Biopsy Combined Gleason Score Primary Gleason Pattern Secondary Gleason Pattern Number of cores (biopsy) Number of positive cores (biopsy) Lobes (Right, Left or Bilateral) Duke Pathology Review (Y or N) Hx of Previous Biopsy (Y or N) PSA Date PSA level T stage Zubrod Baseline AUA Score Baseline AUA Bother score Baseline HEF Baseline

# **Follow-up Data**

ID	Participant	3mo	6mo	12mo	18mo	24mo	36mo
	PSA						
	Date						
	AUA Score
